7.6.1.1	High Grade Treatment-Related Select Adverse Events of Potentially Immune-Mediated Etiology	22
7.6.2	Secondary Analyses	22

7.6.2.1	High Grade Treatment-Related Select Adverse Events of Potentially Immune-Mediated Etiology in Relevant Subgroups	22
7.6.2.2	Select Adverse Events of Potentially Immune-Mediated Etiology	22
7.6.2.3	Immune-Modulating Medications	22
7.6.3	Other Safety Analyses	22
7.6.4	Adverse Events by Standardized MedDRA Query (SMQ)	23
		
		
		
8	CONVENTIONS	25
9	CONTENT OF REPORTS	25
9.1	Clinical Study Report	25
9.2	Other Reports and Reviews	25
9.2.1	Safety Reviews	25
		
10	DOCUMENT HISTORY	26
APPENDIX 1	SELECT ADVERSE EVENTS DEFINITION AND CONVENTIONS	28

		
--	--	--

LIST OF TABLES

Table 2.1-1:	Treatment Phase: Dosing Schedule for Part I.....	8
Table 2.1-2:	Treatment Phase: Dosing Schedule for Part II.....	8
Table 2.4-1:	Protocol Amendments.....	9
Table 4.2.4-1:	Censoring Scheme Used in the Analysis of PFS.....	13
Table 7.4.1-1:	Study Therapy Parameter Definitions	19
Table A-1:	Derivation of clustered select AE	29
Table A-2:	Select Adverse Events.....	31

[REDACTED]

[REDACTED]

- [REDACTED]
- [REDACTED]
- [REDACTED]
- [REDACTED]
- [REDACTED]
- [REDACTED]
- [REDACTED]
- [REDACTED]

[REDACTED]

[REDACTED]

[REDACTED]

[REDACTED]

Schedule of Analyses:

The final analysis will be performed following the database lock after all subjects have completed the study.

During the study, the Scientific Steering Committee (SSC) will closely review the safety data to evaluate the risk/benefit ratio in general and for the separate prospective PS2 subgroup and for subjects treated by ipilimumab monotherapy experienced investigators following a predefined Safety Management Plan.

The Safety Management Plan reviews will include but not be limited to the following frequency and will be triggered by treated patients with ECOG PS2.

- Safety review: Safety review for all treated patients will take place when a minimum of 10 patients in ECOG PS2 subgroup have been dosed with at least 6 weeks of combination regimen therapy (nivolumab combined with ipilimumab) on study to assess safety in all subgroups and evaluate further enrollment into PS2 subgroup.
- Safety review: Safety review for all treated patients will take place when a minimum of 10 patients with at least 12 weeks of combination regimen therapy (nivolumab combined with ipilimumab) on study to assess safety in all treated subjects.
- Subsequent safety reviews: According to the results of previous reviews, further monitoring and subsequent assessments and evaluation of safety will be conducted on a 12-week schedule and data will be provided.

If unexpected events occur, ad hoc telephone conferences with the SSC will be set up.

In addition, a risk/benefit review will be performed for all treated subjects. Initial review for the ECOG PS0-1 subgroup is planned for the first 100 subjects who have been in the study for at least 6 months. According to the results of the safety and risk/benefit reviews, further reviews will be conducted on an as needed basis.

2 STUDY DESCRIPTION

2.1 Study Design

This is a single-regimen, open-label, multicenter, non-randomized, phase 3b study. All patients who meet eligibility criteria will receive the same study treatment regimen. The study consists of three phases: Screening, Treatment, & Follow-up.

The Screening Phase begins by establishing the subject's initial eligibility and signing of the informed consent form. The subject is enrolled using the Interactive Voice Response System (IVRS).

The Treatment Phase begins with the vial assignment call to the IVRS. Study dosing schedules & procedures during the treatment Phase are described as two parts. Part I consists of nivolumab dosing at 1 mg/kg in combination with ipilimumab dosing at 3 mg/kg once every 3 weeks for 12 weeks. Part II consists of nivolumab monotherapy at 3 mg/kg or 240 mg flat dose every 2 weeks until progression or up to a maximum of 24 months of combined study treatment including Part I and Part II. Subject may be treated for more than 24 months for a maximum of 50 cycles in case an on-hold period occurs during the treatment phase. Table 2.1-1 and Table 2.1-2 below describe the schedule for each part of the Treatment Phase of the study.

Table 2.1-1: Treatment Phase: Dosing Schedule for Part I

Every 3 Week Dosing One Cycle = 3 weeks			
Cycle 1	Cycle 2	Cycle 3	Cycle 4
1 mg/kg nivolumab / 3 mg/kg ipilimumab	1 mg/kg nivolumab / 3 mg/kg ipilimumab	1 mg/kg nivolumab / 3 mg/kg ipilimumab	1 mg/kg nivolumab / 3 mg/kg ipilimumab

Table 2.1-2: Treatment Phase: Dosing Schedule for Part II

Every 2 Week Dosing One Cycle = 2 weeks			
Cycle 5	Cycle 6	Cycle 7	Cycle 8 to Cycle 50 (last possible Cycle)
3 mg/kg or 240 mg nivolumab	3 mg/kg or 240 mg nivolumab	3 mg/kg or 240 mg nivolumab	3 mg/kg or 240 mg nivolumab

The Follow-up Phase of the study begins after the conclusion of study treatment.

- Subjects who discontinue therapy in Part I are recommended to be followed by direct contact (office visit) every 4 weeks for up to 100 days after the last dose of combination regimen therapy. After completion of the onsite follow-up visits (for up to 100 days), subjects will be followed every 24 weeks \pm 2 weeks for survival either by direct visit or via telephone contact. OS will be followed from the start of therapy up to 2 years or until death, withdrawal of study consent, or lost-to-follow-up, whichever comes first.
- For subjects who complete or discontinue therapy in Part II, subjects will have 2 follow-up visits (office visits): one approximately 30 days after the last dose of study drug and one approximately 100 days after the last dose of study drug. After completion of the first 2 follow-up visits, subjects will be followed every 24 weeks \pm 2 weeks for survival either by phone contact or direct contact. OS will be followed in accordance to Event Schedule in Protocol from the start of therapy up to 2 years (+ 100 days following the last dose of study treatment), or until death, withdrawal of study consent, or lost-to-follow-up, whichever comes first.
- For subjects who complete therapy in Part II (2 years of treatment), subjects will have 2 follow-up visits (office visits): one approximately 30 days after the last dose of study drug and one approximately 100 days after the last dose of study drug.

2.2 Treatment Assignment

Subjects meeting eligibility criteria will be assigned a subject number via IVRS. No randomization will take place in the study. All subjects will receive the same treatment regimen as described by the study design.

2.3 Blinding and Unblinding

This study is not blinded.

2.4 Protocol Amendments

This SAP incorporates following protocol amendments.

Table 2.4-1: Protocol Amendments

Amendments	Date of Issue	Summary of Major Changes
Revised Protocol 06	31-JUL-2018	
 Follow-up Phase shortened from 5 years after first dose to 2 years after first dose (or 2 years of treatment + 100 days of FU) For patients discontinued in Part I, follow-up visits will be onsite only Contraception wording changed based on updated Investigator's Brochure for nivolumab Changes made to align with nivolumab program standards
Revised Protocol 05	19-Aug-2016	Incorporates Amendment 06
Amendment 06	19-Aug-2016	Incorporates the updated Pulmonary, Renal, and Skin Adverse Event Management Algorithms that were mistakenly not included in the Revised Protocol associated with Amendment 05.
Revised Protocol 04	03-Aug-2016	Incorporated Amendment 05 and Administrative Letter 02
Amendment 05	03-Aug-2016	
 To revise the Management Algorithms to align with the new recommendations To align with the nivolumab program standards, including changes to the duration of contraception use To address minor inconsistencies in the protocol To clarify that tumor assessments beyond Week 12 should be made according to the investigator's assessment.
Administrative Letter 02	28-Jun-2016	
 Update the address of the Bristol-Myers Squibb Research and Development facility where the Medical Monitor is located Clarify that the lettered numbering of the Inclusion Criteria was inadvertently re-numbered during the creation of the revised protocol associated with Amendment 04 Clarify the Dose Delay Criteria for Grade 2 drug-related creatinine, aspartate aminotransferase, alanine aminotransferase, or total bilirubin Clarify that tumor scans should also be completed for subjects who discontinue during the nivolumab and ipilimumab combination part (Part I) of the trial.
Revised Protocol 03	25-May-2016	Incorporated Amendment 04 and Administrative Letter 01
Amendment 04	25-May-2016	
 Changes the nivolumab monotherapy dose in Part II to 240 mg flat dose for those subjects who enroll after the implementation of Amendment 04 Decreases the infusion times of nivolumab and ipilimumab Adds the collection and analysis of biomarkers
Administrative Letter 01	22-Mar-2016	
 Align chemistry laboratory procedures throughout the screening, treatment, and follow-up phases and to remove the term serum from these procedures.

Table 2.4-1: Protocol Amendments

Amendments	Date of Issue	Summary of Major Changes
		
 Align timing of receipt of testing results and dosing between the Time and Events Schedules and Section 5.3, Safety Assessments. Add footnotes to Table 5.1-2, On Study Assessments Part I: Cycles 1 through 4 (Nivolumab Plus Ipilimumab) and Table 5.1-3, On-Treatment Assessments Part II: Cycles 5 and Beyond (Nivolumab Monotherapy) to clarify that procedures for each time point should also be delayed if the dose is delayed Clarify that investigators should follow the Management Algorithms in Appendix 1 for all grade adverse events rather than only Grades 3-4 in the Notes sections of Tables 5.1-2, On-Study Assessments Part I: Cycles 1 through 4 (Nivolumab Plus Ipilimumab) and 5.1-3, On-Treatment Assessments Part II: Cycles 5 and Beyond (Nivolumab Monotherapy). Remove dosing windows Tables 5.1-2, On-Study Assessments Part I: Cycles 1 through 4 (Nivolumab Plus Ipilimumab) and 5.1-3, On-Treatment Assessments Part II: Cycles 5 and Beyond (Nivolumab Monotherapy). Add windows to Table 5.1-4, Follow Up Assessments for Subjects who Discontinue in Part I Align the footnotes and Notes section related collection of adverse events in Tables 5.1-4, Follow Up Assessments for Subjects who Discontinue in Part I and 5.1-5, Follow-Up Assessments for Subjects who Discontinue in Part II to each other for consistency. Remove the “Every 4 Week Column” from Table 5.1-5, Follow-Up Assessments for Subjects who Discontinue in Part II Provide clarity on the timing of dosing when lipase test results are not available prior to dosing in Section 5.3, Safety Assessments. Provide clarity on the timing of dosing in relation to receipt of test results as it differs for baseline assessments and on-treatment assessments.
Revised Protocol 02	05-Feb-2016	Incorporated Amendment 02
Amendment 02	05-Feb-2016	Removed Human Immunodeficiency Virus (HIV) or Acquired Immunodeficiency Syndrome Exclusion Criterion
Revised Protocol 01	06-Jan-2016	Incorporated Amendment 01
Amendment 01	06-Jan-2016	
 Changes Exclusion Criteria to known history of Human Immunodeficiency Virus (HIV) or Acquired Immunodeficiency Syndrome and removes HIV testing from the screening procedures. Adds the definition of a Suspected Unexpected Serious Adverse Event Requires local regulatory approval if applicable prior implementation of deviations or changes to the protocol.
Original Protocol	03-Jun-2015	Not applicable

3 OBJECTIVES

3.1 Primary

The primary objective of this study is to determine the incidence of high-grade (CTCAE v4.0 Grades 3-5), treatment-related, select adverse events of potentially immune-mediated etiology (pulmonary, gastrointestinal, skin, renal, hepatic, endocrine, infusion related, or hypersensitivity) of nivolumab plus ipilimumab combination regimen as first-line therapy for unresectable or metastatic melanoma.

3.2 Secondary

The secondary objectives of this study are:

- To determine the incidence and to characterize the outcome (duration of serious adverse event [SAE] treatment, dose of immune-modulating agents [ie, steroids] used, time to event onset, and event resolution, and worst grade of event) of high-grade (CTCAE v4.0 Grade 3 or higher), select adverse events of potentially immune-mediated etiology in subjects with unresectable or metastatic melanoma treated with nivolumab and ipilimumab combination regimen.
- To estimate OS in all treated subjects
- To assess safety, tolerability, investigator-assessed objective response rate (ORR), progression-free survival (PFS), and OS in all subjects and in certain subsets of subjects (ECOG PS0-1, ECOG PS2, ocular/uveal, cutaneous, and mucosal melanoma, brain metastasis)

[REDACTED]

4 ENDPOINTS

4.1 Primary Endpoint

The primary endpoint is the incidence of high-grade (CTCAE v4.0 Grade 3-5), treatment-related, select adverse events of potentially immune-mediated etiology (pulmonary, gastrointestinal, skin, renal, hepatic, endocrine, infusion related or hypersensitivity). Select adverse events of potentially immune-mediated etiology are identified using a custom MedDRA query that is fully defined/updated by BMS and maintained as a separate file (Table A-2). The most recent version will be used for the analysis.

4.2 Secondary Endpoints

The secondary endpoints include those endpoints further relating to the safety and tolerability of the treatment regimen. Also included are response rates, progression, and survival times as described in this Section.

4.2.1 Adverse Events

The incidence of all AEs, treatment-related AEs, serious AEs, and deaths are among the secondary endpoints. In addition, the incidence of all high-grade (Grades 3-5), select adverse events (such as pulmonary, gastrointestinal, skin, renal, hepatic, endocrine, and infusion-related or hypersensitivity) of potentially immune-mediated etiology will be analyzed along with the median time to onset and median time to resolution of select adverse events. Resolution of an AE is a subject experiencing complete resolution or improvement to the baseline grade for the AE.

4.2.2 Laboratory Tests

The rate of subjects experiencing laboratory test abnormalities and the change in results over the course of the study are among the secondary endpoints for the types of tests below.

- Complete blood counts with differentials
- Serum chemistry tests
- Liver function tests
- Thyroid function testing

4.2.3 Overall Survival

OS will be until death, withdrawal of study consent, or lost to follow-up for up to 2 years from the first dose of study treatment. OS is defined as the time between the start of treatment and the date of death due to any cause. A subject who has not died will be censored at last known date alive. $OS = (\text{date of death/last known date alive} - \text{first dose date})/30.4375$ (months).

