For Part I, nivolumab and ipilimumab are administered every 3 weeks for 4 doses (Table 5.1-2). If subjects discontinue therapy during Part I, nivolumab monotherapy can be continued as

described in [Section 4.5.5](#). **For Part II**, nivolumab monotherapy is administered every 2 weeks ([Table 5.1-3](#)) until 24 months after the first combination dose (Part I and II). Subjects may be treated for more than 24 months for a maximum of 50 cycles in case an on-hold period occurs during the Treatment Phase.

Windows for dosing of both Part I and Part II are discussed in [Section 4.5](#).

An initial tumor assessment is to be completed at Week 12 (± 5 days) after the first treatment dose. Further tumor assessments are recommended to be completed as required by local standards of care or at the investigator's discretion and are recommended every 8 weeks until documented tumor progression.

Subjects treated with the study drugs will be permitted to continue treatment beyond initial PD as assessed by the investigator's clinical judgment and local standards of care as long as they meet the criteria specified in [Section 4.5.8](#).

The Treatment Phase ends when the subject is discontinued from study therapy. For a complete list of reasons for treatment discontinuation, see [Sections 3.5](#) and [4.5.6](#).

The Follow-up Phase begins when the decision to discontinue a subject from study therapy is made (no further treatment with study therapy) ([Table 5.1-4](#) and [Table 5.1-5](#)):

- Subjects who discontinue therapy in Part I are recommended to be followed by direct contact (office visit) every 4 weeks for up to 100 days after the last dose of combination regimen therapy. After completion of the onsite follow-up visits (for up to 100 days), subjects will be followed every 24 weeks ± 2 weeks for survival either by direct visit or via telephone contact. OS will be followed from the start of therapy up to 2 years or until death, withdrawal of study consent, or lost-to-follow-up, whichever comes first.

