3.6 Post Study Drug Study Follow up

BMS may request that survival data be collected on all treated participants outside of the protocol-defined window (see [Section 5.1](#), Flow Chart/Time and Events Schedule). At the time of this request, each participant will be contacted to determine their survival status unless the participant has withdrawn consent for all contacts or is lost to follow-up.

In this study, safety is a key endpoint of the study. Post-study follow-up is of critical importance and is essential to preserving subject safety and the integrity of the study. Subjects who discontinue study drug must continue to be followed for collection of outcome and/or survival follow-up data as required and in line with [Section 5](#) until death or the conclusion of the study. The Follow-up Phase is described in [Table 5.1-4](#) and [Table 5.1-5](#).

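### OS follow-up limits conflict and no closing vital-status check is scheduled, so the OS curve from about month 19-20 is at risk of informative censoring

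*SAP*

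**What the plan says.** **End of OS follow-up.**
- SAP 4.2.3 gives one limit for everyone, "for up to 2 years from the first dose of study treatment". The survival row of Protocol Table 5.1-5 also gives 2 years from first dose.
- SAP 2.1 gives two limits. For subjects who stop in Part I: "OS will be followed from the start of therapy up to 2 years or until death, withdrawal of study consent". For Part II subjects follow-up runs "from the start of therapy up to 2 years (+ 100 days following the last dose of study treatment"). Protocol 3.1 and 5.3 make the same split, and the footnote to Table 5.1-5 also adds the 100 days.
- Protocol 5.4 and the assessments text of the synopsis add the 100 days without separating Part I from Part II.

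**Censoring.** SAP 4.2.3: "A subject who has not died will be censored at last known date alive". The OS formula there uses that date with no truncation. The schedule of analyses in the SAP places the final analysis after all subjects have completed the study and sets no OS cut-off.

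**Contacts.** Protocol 3.1, for Part I stoppers: "After completion of the onsite follow-up visits (for up to 100 days), subjects will be followed every 24 weeks" (window 2 weeks either side). Part II subjects have visits at about 30 and 100 days after last dose and then the same 24-week cycle. The only contact outside this cycle that covers everyone is in Protocol 3.6: "BMS may request that survival data be collected on all treated participants outside of the protocol-defined window". It is optional and undated.

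**Analysis.** SAP 7.5.2 plans Kaplan-Meier curves and medians with 95% confidence intervals, overall and by subgroup.

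**The concern.** A Kaplan-Meier curve is valid if, at each time, the subjects censored have the same prospects as those still followed. Two features of the plan put this at risk late in follow-up.

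1. The 24-week cycle starts from the last dose, so it reaches month 24 only by chance. A survivor is censored at the last contact before the limit. A death in the remaining gap has an exact date and can enter the curve if the site hears of it. Deaths and survivors may then be ascertained differently.
2. Subjects still on treatment near month 24 are alive at that point by construction, and they are followed about 100 days longer. Without truncation they alone make up the risk set beyond month 24.

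In both cases the time of censoring depends on treatment duration, which is likely to be prognostic. Estimating OS in all treated subjects is a stated secondary objective. The planned subgroups (ECOG performance status, brain metastasis, disease subtype) may differ in treatment duration and so be observed differently.

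**Working it through.** **The plan's own figures.** The visible text gives no expected OS, event count or precision for OS. The only precision figure belongs to the primary endpoint: 308 of 615, 95% CI 46.06% to 54.11%. It reproduces as an exact Clopper-Pearson interval and plays no part below.

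**Step 1: contact calendar.** Inputs: Part I doses every 3 weeks (Days 0, 21, 42, 63); Cycle 5 three weeks after Cycle 4 (Day 84), then every 14 days; follow-up to 100 days after last dose; then every 168 days. Contact day = last dose + 100 + 168k, compared with Day 730.

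| Last dose | 100-day point | Later contacts by Day 730 | Gap to Day 730 | Next contact |
|---|---|---|---|---|
| Day 0 | 100 | 268, 436, 604 | 126 days (18 wk) | 772 |
| Day 21 | 121 | 289, 457, 625 | 105 days (15 wk) | 793 |
| Day 42 | 142 | 310, 478, 646 | 84 days (12 wk) | 814 |
| Day 63 | 163 | 331, 499, 667 | 63 days (9 wk) | 835 |
| Day 84 (Cycle 5) | 184 | 352, 520, 688 | 42 days (6 wk) | 856 |
| Day 140 (Cycle 9) | 240 | 408, 576 | 154 days (22 wk) | 744 |

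The 2-week window on the last contact changes 9-18 weeks to 9 - 2 = 7 up to 18 + 2 = 20 weeks. Dose delays can move the gap anywhere from about 0 to 24 weeks. A last dose on Day 126 gives 226, 394, 562, 730 (gap 0). One on Day 147 gives 247, 415, 583 (gap 147 days, 21 weeks).

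The earliest affected time is 604/30.4375 = month 19.8 for on-time Part I stoppers and 576/30.4375 = month 18.9 for the Cycle 9 example.

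**Step 2: who is followed past month 24.** Cycle 50 without delay is on Day 84 + 45 × 14 = 714. Adding 100 gives Day 814, or month 26.7. A last dose on Day 730 gives Day 830, or month 27.3. For a Part I stopper, last dose + 100 days is Day 100 to 163, so the added 100 days, read literally, extend nothing.

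**Step 3: size near month 24 (assumptions, not document figures).** Simulation of 400,000 subjects in each of 8 scenarios:
- 30-50% stop in Part I, 20% are treated to week 102, and the rest stop evenly between weeks 12 and 100.
- Survival is exponential, from first dose for Part I stoppers and from last dose for the others.
- Medians are 12-36 months (Part I stoppers), 12-24 (early Part II stoppers) and 24-60 (long-treated).

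| Deaths after last scheduled contact | Error at month 23.9 | Error at month 26 |
|---|---|---|
| Not learned | +1.6 to +3.0 points | +1.8 to +5.3 points |
| Learned, survivors censored at last contact | -4.0 to -5.4 points | -1.7 to -4.9 points |
| Everyone checked at month 24, OS truncated there | 0 | not estimated |

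In these scenarios 52-75% of subjects are alive at month 24, but only about 23-24% of all subjects are followed beyond it. In the scenario with a true median of 25.0 months, the estimated median was 23.5 months with gap deaths learned and was not reached with them unlearned.

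**Step 4: a simple picture beyond month 24.** Assume that 20% of survivors are long-treated with monthly hazard 0.005, and the rest have 0.02. Over 100/30.4375 = 3.29 months:
- Shown by the curve (long-treated only): exp(-0.005 × 3.29) = 98.4%.
- True for all: 0.2 × 98.4% + 0.8 × exp(-0.02 × 3.29) = 0.2 × 98.4% + 0.8 × 93.6% = 94.6%.

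**The case against.** - **A common limit exists.** A reader might infer that OS has no common end of follow-up. The documents do not support that: SAP 4.2.3 states one 2-year limit. The defect is that other sections contradict it and that no truncation rule enforces it.
- **Not a Part I problem alone.** A reader might contrast Part I stoppers with Part II subjects. Early Part II stoppers are on the same 24-week cycle and have similar gaps. The relevant contrast is early stopping against long treatment.
- **Other contacts can shorten the gap.** Subjects with ongoing drug-related adverse events are followed beyond 100 days (Table 5.1-4, footnote a). Those who stopped for reasons other than progression continue tumor assessments by local standard for up to 2 years. Protocol 3.6 speaks of follow-up to the conclusion of the study and allows a survival request, and 3.6.1 and 3.6.2 allow public sources. This stands, so the bias is a risk, not a certainty. But the adverse-event and tumor contacts cover selected subjects, and the request that would cover everyone is discretionary.
- **Size and sign are assumed.** This stands. If the gap is confined to Part I stoppers and everyone else is treated as fully observed, the range shrinks to about 0 to +1.6 points or -0.7 to -3.4 points. For comparison, the sampling 95% half-width at 60% survival with 615 uncensored subjects is 1.96 × √(0.6 × 0.4/615) = 3.9 points. The confidence interval does not, however, cover this bias.
- **OS is secondary and descriptive.** This stands. The visible text names no 24-month rate, and the curve before about month 19 is untouched.

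**Conclusion.** The plan contains conflicting OS follow-up limits, censoring at last known date alive without truncation, and no scheduled vital-status check at month 24. Following it as written can leave early stoppers without a scheduled survival contact before month 24: nominally 9-18 weeks for on-time Part I stoppers, and about 0-24 weeks once windows and delays are allowed for. Only long-treated subjects are followed to about month 27.

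The part of the Kaplan-Meier OS curve from about month 19-20 onward is therefore at risk of informative censoring. The median is affected only if it falls there, and the documents give no expected median. The likely size is a few percentage points under assumed stopping rates and survival. The direction depends on whether gap deaths are learned.

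A reader might go further and conclude that the 24-month survival result is biased, or that the main result of the trial is compromised. The documents support neither. The sponsor may run the survival sweep in Protocol 3.6, which could close the gap. The primary endpoint is adverse-event incidence, and neither it nor the sample size depends on OS follow-up.

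**What to change.** 1. Make the survival request in Protocol 3.6 a planned step. Add to Tables 5.1-4 and 5.1-5 one vital-status check, by phone or permitted public record, at or shortly after Day 730 for every treated subject not known to have died, within the consent limits of Protocol 3.6 and 3.6.1.
2. In SAP 4.2.3, censor OS administratively at Day 730, consistent with that section's own 2-year definition. List later deaths separately.
3. Align the OS follow-up wording in SAP 4.2.3 and 2.1, Protocol 3.1, 5.3 and 5.4, the row and footnote of Table 5.1-5, and the synopsis. The 100-day safety follow-up need not change.

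A common calendar cut-off combined with the same sweep would also work and would keep later deaths, but it needs current vital status for everyone at that date.

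Cost: one call or registry check per surviving subject, plus wording changes. Deaths after Day 730 do not enter the curve, and a median beyond month 24 would be reported as not reached.
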